6.1.1. All Adverse Events

The verbatim terms used in the CRF by investigators to identify AEs will be coded using the Medical Dictionary for Regulatory Activities (MedDRA), version 19.0 or higher. These coded AE terms are referred to as preferred terms (PT); classification into System Organ Class (SOC) is a result of the coding process.

Treatment-emergent AEs (TEAEs) are defined as 1) those that occur in TEAE period as defined below 2) present before first dose, but worsened in toxicity grade during treatment; 3) had missing start date and its end date is during the treatment; 4) was a drug-related event. Drug-related AEs are those assessed by investigator as being possible, probable, or very likely

related to study drug. To determine TEAE, partially missing AE start dates will be imputed according to the rules stated in Section [2.7](#).

For each TEAE, the percentage of subjects who experience at least 1 occurrence of the given event will be summarized. Tables will be sorted by frequency in incidence (the highest to lowest incidence).

For subjects using CYP3A inhibitor during treatment-emergent period, all TEAEs will be summarized by SOC, PT, maximum severity, any CYP3A inhibitor (Yes vs. No), and strong CYP3A inhibitor (Yes vs. No).

Treatment-Emergent Period

In general, the treatment-emergent period is defined as the time from first dose date through 30 days after last dose date, or day before subsequent antilymphoma therapy or a conditioning regimen for stem cell transplantation, whichever occurs first.

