6. DOSAGE AND ADMINISTRATION

For the purposes of this study, 'study drug' refers to ibrutinib and 'study treatment' refers to ibrutinib and CIT. The dosages for background CIT are described in [Table 5](#) and [Table 6](#). A dosing guide for ibrutinib is provided in [Attachment 1](#). For subjects who require dosing through a feeding tube please refer to the Investigational Product Preparation Instruction (IPPI) for information on compatible tubes. All dosing information must be recorded in the Dosage Administration page of the case report form (CRF).

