11.7. Safety Analyses

All safety analyses will be based on the safety population and will be performed by the treatment actually received. Safety parameters to be evaluated are the incidence, intensity, and type of adverse events, clinically significant changes in the subject's physical examination findings and clinical laboratory results by treatment arms. Exposure to investigational product and reasons for discontinuation of study treatment will be tabulated.

Adverse Events

The verbatim terms used in the CRF by investigators to identify adverse events will be coded using the Medical Dictionary for Regulatory Activities (MedDRA). All reported adverse events will be included in the analysis.

Treatment-emergent adverse events are adverse events with onset during the Treatment Phase or that are a consequence of a pre-existing condition that has worsened since baseline, and occur during treatment or within 30 days following the last dose of study treatment, or any adverse event that is considered study treatment-related regardless of the start date of the event. The number and percent of subjects with treatment-emergent adverse events will be summarized according to intensity using the National Cancer Institute (NCI) Common Terminology Criteria for Adverse Events (CTCAE) (Version 4.03), drug relationship, and outcome. For each adverse event, the percentage of subjects who experience at least 1 occurrence of the given event will be summarized by treatment group. In addition, comparisons between treatment groups will be provided if appropriate. Summaries, listings, datasets, or subject narratives may be provided, as appropriate, for those subjects who die, who discontinue treatment due to an adverse event, or who experience a severe or a serious adverse event.

Clinical Laboratory Tests

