14. STUDY DRUG INFORMATION

For the purposes of this study, 'study drug' refers to ibrutinib.

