1.5. Randomization and Blinding

Central randomization will be implemented in Part 2 of this study. Subjects will be randomly assigned to 1 of 2 treatment groups based on a computer-generated randomization schedule prepared before the study by or under the supervision of the sponsor. The randomization will be balanced by using randomly permuted blocks and will be stratified by histology and background therapy, then randomized in a 2:1 ratio to either Treatment Arm A (ibrutinib and RICE or RVICI background therapy) or Treatment Arm B (RICE or RVICI background therapy only). The interactive web response system (IWRS) will assign a unique treatment code, which will dictate the treatment assignment and matching study drug kit for the subject. The requestor must use his or her own user identification and personal identification number when contacting the IWRS, and will then provide the relevant subject details to uniquely identify the subject.

As this is an open-label study, blinding procedures are not applicable.

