6.3. Deaths

A summary of the number of deaths during the treatment phase and up to 30 days after last dose will be provided, along with the primary cause of death. In particular, frequencies of deaths due to study treatment-related adverse events will also be reported. A death is study medication-related death if the primary cause is a drug related AE.

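### The SAP ties related adverse events to study drug, which the protocol defines as ibrutinib alone; read literally, the CIT-only arm can have no related events or related deaths

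*SAP*

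**What the plan says.** SAP 6.1.1 sets the rule in one sentence that runs on from "Drug-related AEs are those assessed by investigator as being possible, probable, or very likely" to "related to study drug. To determine TEAE, partially missing AE start dates will be imputed". The same section makes being a drug-related event the fourth, free-standing way to qualify as treatment-emergent. SAP Table 4 then ticks a drug-related version of five outputs: the overall summary, all TEAEs, serious TEAEs, Grade 3 or worse TEAEs, and TEAEs leading to discontinuation.

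For deaths, SAP 6.3 promises frequencies of study treatment-related deaths and then gives the classifying rule: "A death is study medication-related death if the primary cause is a drug related AE".

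The SAP does not say what study drug means. Protocol Section 6 does: "For the purposes of this study, 'study drug' refers to ibrutinib and 'study treatment' refers to ibrutinib and CIT". Protocol Section 14 repeats it: "For the purposes of this study, 'study drug' refers to ibrutinib". The control group, in SAP 1.5, is "Treatment Arm B (RICE or RVICI background therapy only").

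The protocol's own definition of a treatment-emergent event, in Section 11.7, uses the wider term. It admits events in the treatment window "or any adverse event that is considered study treatment-related regardless of the start date of the event".

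**The concern.** This is an add-on trial in which both arms receive intensive CIT, and safety is the first secondary objective listed for Part 2. A by-arm table of related events informs the reader only if an event can be called related in either arm. If related means related to ibrutinib, the control column is empty by construction. A count in the ibrutinib arm would then be set against a zero that says nothing about how toxic the control regimen was. The same holds for related deaths.

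Attribution to ibrutinib alone is also fragile in the ibrutinib arm. Protocol 6.2.2 concedes that hematologic toxicity is expected with both CIT regimens and that its relation to ibrutinib may not be separable.

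Finally, the SAP's fourth TEAE criterion, read this way, departs from protocol 11.7. SAP Section 9, headed as the place for changes to protocol-specified analyses, shows no entry for it.

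**Working it through.** No figure in the plan depends on this rule, so the check traces terms through the two documents.

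1. Drug-related means related to study drug (SAP 6.1.1).
2. Study drug means ibrutinib (protocol Sections 6 and 14).
3. Arm B receives no ibrutinib (SAP 1.5), and safety is summarised by arm as treated (SAP Section 6).
4. So on the protocol's definition no Arm B event can be drug-related.
5. A related death needs a drug-related AE as its primary cause (SAP 6.3), so Arm B can have no related death.

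The number of subjects concerned, by the plan's own figures (SAP 1.4), is 72 − 48 = 24 controls. That is planned full enrollment. Protocol 11.9.1 reports that enrollment stopped at the interim analysis, and protocol Table 11 had projected 46 subjects by then. At 2:1 that is 46 ÷ 3 ≈ 15 controls. The documents do not give the number actually randomized.

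The two readings side by side:

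| Item | Related to ibrutinib only (SAP 6.1.1 with the protocol's definition) | Related to any study treatment (protocol 11.7) |
|---|---|---|
| Related TEAEs, Arm A | Only those at least possibly due to ibrutinib | Those due to ibrutinib or CIT |
| Related TEAEs, Arm B | None possible | Those due to CIT |
| Related deaths, Arm B | None possible | Those due to CIT |
| Late event attributed to CIT alone | Not admitted by criterion 4 in either arm | Admitted in both arms |
| Late event attributed to ibrutinib | Admitted; Arm A only | Admitted; Arm A only |

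Late here means after the treatment-emergent period of SAP 6.1.1, which ends 30 days after the last dose or earlier if subsequent therapy starts. Protocol 12.3.1 requires events after 30 days to be reported when related to study treatment. Late CIT-related events would therefore be collected and then not qualify under criterion 4.

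Whether the data would support the wider reading depends on what investigators record, and the protocol is not consistent. Section 9.8 asks for the relationship to study drug. Section 12.3.1 asks for the relationship to study treatment and, later in the same paragraph, to study therapy.

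**The case against.** The strongest reply is that the SAP does not use study drug to mean ibrutinib alone. SAP 2.3.2 analyses the whole safety set, CIT-only subjects included, by the study drug actually received. SAP 4.6 ends the concomitant-medication window at the last dose of study drug; read literally, that leaves controls without a window, which nobody can have intended. SAP 4.4 lists ibrutinib and every CIT drug as study medications. SAP 6.3 speaks of study treatment-related and study medication-related deaths before it reaches the phrase drug related AE. The discontinuation row of Table 4 is labelled for both regimens. The protocol is loose too: Section 14.3 mentions centrally supplied CIT under study drug. If causality is recorded as Section 12.3.1 says, control events can be flagged as related.

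This stands as far as it goes. A reader might infer that the control arm will certainly show zero related events. The documents do not settle that; they support it only as the literal reading. But the loose usage does not repair the rule. It leaves a programmer with two defensible readings that give opposite control columns, and the only explicit definition favours the narrow one.

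The impact is also bounded. All-cause TEAEs, serious TEAEs, Grade 3 or worse TEAEs, fatal TEAEs and deaths within 30 days are all planned by arm. They do not depend on attribution, except for late events entering through criterion 4. SAP Section 6 plans no inferential safety statistics.

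**Conclusion.** The related-event rule in SAP 6.1.1 and 6.3 is wrong as written and should be corrected. Applied with the protocol's definition, it allows no related AEs and no related deaths in the CIT-only arm, and it narrows the protocol's treatment-emergent definition for late events. The effect falls on five drug-related outputs, the related-death count and, for late events only, the TEAE tables. It does not touch the efficacy analysis.

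Two stronger inferences should be resisted.

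- It is tempting to say that late CIT toxicity counts only in the ibrutinib arm. On the literal reading, an event attributed to CIT alone drops out of both arms; the asymmetry is confined to late events attributed at least possibly to ibrutinib.
- It is tempting to size the distortion, for example as a near-universal rate of CIT-related severe events, or one or two toxic deaths among 24 controls, shown as none. Protocol 1.2 does describe severe myelosuppression in almost all subjects of a RICE study, but that study had 20 evaluable subjects and no RVICI, and it reported no deaths from infection. The documents give no CIT-related mortality for this trial. Assuming 5% to 10% gives 0.05 × 24 = 1.2 to 0.10 × 24 = 2.4 deaths, and that is illustration only.

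The conclusion assumes that the protocol's definitions govern terms the SAP leaves undefined.

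**What to change.** - In SAP 6.1.1, define a related AE as one judged possibly, probably or very likely related to any component of study treatment (ibrutinib or CIT), in both arms.
- Use that definition for TEAE criterion 4, for every between-arm related-event table and for related deaths in SAP 6.3. Use one term throughout 6.3. This brings the SAP into line with protocol 11.7.
- Show ibrutinib-related events in a separate table, for the ibrutinib arm only.
- Reconcile protocol 9.8 (relationship to study drug) with 12.3.1 (relationship to study treatment), and confirm which causality field the CRF holds.

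If the CRF follows 12.3.1, the cost is SAP wording and table shells. If it holds only the relationship to ibrutinib, the relationship to CIT would have to be obtained from the sites. Failing that, the by-arm related tables should be dropped and the comparison left to the all-cause tables.

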The Treatment Phase will extend from enrollment (in Part 1) or randomization (in Part 2) until 1 of the following: 1) completion of 3 cycles of therapy, 2) transplantation, if clinically indicated, or 3) PD, whichever comes first. Cycles will be 28 days long; however, if count recovery occurs quickly and the investigator deems a subject ready to proceed with the next cycle of therapy, cycles can be shortened to as few as 21 days. As long as there is no disease progression after Cycle 1 or 2, a second and third cycle of therapy will be given, respectively. All subjects will receive background therapy with RICE or RVICI during the Treatment Phase.

The investigator will evaluate sites of disease by radiological imaging, physical examination, or other procedures as necessary, including but not limited to review of hematology, clinical chemistry, and lumbar puncture results. Assessment of tumor response and progression will be according to the International Pediatric NHL Response Criteria. The primary efficacy analysis of EFS will be based on assessment by an Independent Review Committee (IRC). At each site visit, subjects will undergo safety evaluations. Safety evaluations will include adverse event monitoring, physical examinations, concomitant medication usage, and clinical laboratory parameters. Population pharmacokinetics will be performed during Part 1 using a sparse sampling approach. Additional sparse pharmacokinetic samples will be collected during Part 2 to expand the pediatric pharmacokinetic dataset. Blood samples will be obtained for pharmacodynamic assessments (BTK occupancy) and for protein binding (Part 1 only).

[figure not shown]
Subjects will begin the Posttreatment Phase after completion of combination therapy. During the Posttreatment Phase, subjects on ibrutinib having a response of PR or better and have completed 3 cycles of combination treatment will continue on ibrutinib monotherapy at the same daily dose for three 28-day cycles, or until disease progression or unacceptable toxicity, or up until initiating subsequent antilymphoma therapy or a conditioning regimen for stem cell transplantation, whichever comes first. Follow-up visits to assess disease progression will be required if study treatment is discontinued prior to PD (including subjects who go on to transplant) and will be completed as per [Table 3](#) and [Table 4](#) until PD, the clinical cutoff for the

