Subjects will be randomized in a 2:1 ratio to Treatment Arm A (ibrutinib 329 mg/m² or other dose as determined in Part 1, and RICE or RVICI background therapy) or Treatment Arm B (RICE or RVICI background therapy only). Study treatment administration begins on Cycle 1 Day 1 and ends on the last day of Cycle 3, unless the subject experiences unacceptable toxicity or disease progression. Cycles will be 28 days long; however, if count recovery occurs quickly, cycles can be truncated to as few as 21 days. As long as there is no disease progression after Cycle 1 or 2, a second and third cycle of therapy will be given, respectively. Upon completion of 3 cycles of combination therapy, subjects randomized to ibrutinib having a response of PR or better will continue on ibrutinib monotherapy at the same daily dose for three 28-day cycles or until disease progression or unacceptable toxicity, or up until initiating subsequent antilymphoma therapy or a conditioning regimen for stem cell transplantation, whichever comes first.

Ibrutinib will be supplied as capsules or as a suspension and will be self-administered at home on each day of each cycle. Study-site personnel will instruct subjects on how to store ibrutinib for at-home use as indicated for this protocol. Subjects randomized to ibrutinib will be asked to keep a log of medication administration and report dietary intake on PK days.

The amount (in mg) of all study treatment to be administered will be determined by BSA ([Attachment 3](#)). Dosing guides for capsule and suspension administration are provided in [Attachment 1](#). If a subject experiences a >10% change in weight from the weight used in the previous BSA calculation, then the BSA and dose should be recalculated.

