6.1. Adverse Events

Table 4 provides a summary of adverse events analyses to be performed.

Table 4: Summary of Adverse Event Analyses to be Performed

Category	Analysis	Sorted By	Cut off	Drug-Related TEAE
General	Overall summary			✓
	TEAEs	SOC+ PT+ toxicity grade; PT+ toxicity grade	10%, 5%	✓
	Serious TEAEs	SOC+ PT + toxicity grade; PT+ toxicity grade	2%	✓
	Grade 3 or worse TEAE	PT+ toxicity grade	2%	✓
	TEAEs leading to treatment discontinuation (ibrutinib+CIT/CIT)	PT + toxicity grade		✓
	TEAEs leading to death	PT + toxicity grade		
	TEAEs leading to dose modification or modification (ibrutinib+CIT/CIT)	PT + toxicity grade		
	AEs of clinical interest (Hemorrhagic events)	PT + toxicity grade		
	Other safety observations (eg, other malignancies, eye disorder)	PT + toxicity grade		
	Deaths within 30 days of last dose	Reason for death		
Subgroup	Overall summary			
	TEAEs	SOC+ PT+ toxicity grade		
Exposure adjusted incidence rate	Overall summary			
	TEAEs	SOC+ PT+ toxicity grade; PT+ toxicity grade	1 per 100 patient month	
	Serious TEAEs	SOC+ PT + toxicity grade; PT+ toxicity grade	0.1 per 100 patient month	

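### The treatment-emergent window ends at about Day 95 for control completers but at Day 114 to 198 on ibrutinib, and no planned safety table compares the arms over a common period

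*SAP*

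**What the plan says.** SAP 6.1.1 defines a single treatment-emergent period for both arms: "the treatment-emergent period is defined as the time from first dose date through 30 days after last dose date". The period closes sooner when new treatment starts, under a second clause that reads "or day before subsequent antilymphoma therapy or a conditioning regimen for stem cell transplantation, whichever occurs first".

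Dosing stops at different times in the two arms. Protocol 6.1 gives both arms three cycles: "Cycles will be 28 days long; however, if count recovery occurs quickly, cycles can be truncated to as few as 21 days". Ibrutinib is taken every day of each cycle, whereas the last scheduled CIT dose is dexamethasone on Day 9 (Protocol Tables 5 and 6). Ibrutinib subjects who respond then go further: Protocol 6.1 says that they "will continue on ibrutinib monotherapy at the same daily dose for three 28-day cycles or until disease progression or unacceptable toxicity". Monotherapy also stops when new therapy or conditioning begins. Protocol 3.1 limits this to "subjects on ibrutinib having a response of PR or better and have completed 3 cycles of combination treatment". Protocol 9.8 states that adverse event collection extends past monotherapy.

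SAP Table 4 plans percentages of subjects with at least one event, plus a block headed "Exposure adjusted incidence rate" that covers the overall summary, TEAEs and serious TEAEs. Grade 3 or worse events, hemorrhage and deaths have no adjusted version. SAP 6.3 adds: "A summary of the number of deaths during the treatment phase and up to 30 days after last dose will be provided". Neither document plans an adverse event table by phase or over a common window, and the SAP does not define the denominator of the adjusted rates.

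Protocol 11.7 words the definition differently. It ties the onset of a treatment-emergent event to the Treatment Phase, which under Protocol 3.1 ends in both arms at three cycles, transplantation or progression. SAP Section 9, on changes from the protocol, has no content.

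**The concern.** Safety and tolerability of the combination is a Part 2 secondary objective, and SAP Section 6 plans no inferential statistics on safety. The descriptive tables are therefore the whole safety comparison.

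If one arm is observed for longer, the proportion with at least one event rises in that arm even when the drug adds nothing. Dividing by exposure time corrects this only if risk is roughly constant. If most toxicity falls in the CIT cycles, the later monotherapy time adds person-months with few events and pulls the ibrutinib rate down. A reader would then have one table that tends to err against ibrutinib, another that may err in its favour, and no like-for-like table to settle the matter.

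**Working it through.** **Reproducing a stated figure.** Neither document states a window length in days or an expected adverse event rate, so there is no plan figure to reproduce. The one input that can be checked is the last CIT day: dexamethasone 20 mg/m²/day on Days 5 to 9 gives 20 × 5 = 100 mg/m² per cycle, which agrees with the cumulative dose in the protocol synopsis.

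**Window length** (last scheduled dose day + 30), for subjects who complete three cycles without an early cut. I take last dose to include monotherapy, as Protocol 9.8 does; SAP 6.1.1 does not say so expressly.

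| | 28-day cycles | 21-day cycles |
|---|---|---|
| Control | 56 + 9 + 30 = 95 | 42 + 9 + 30 = 81 |
| Ibrutinib, no monotherapy | 84 + 30 = 114 (ratio 1.20) | 63 + 30 = 93 (1.15) |
| Ibrutinib, all monotherapy | 84 + 84 + 30 = 198 (2.08) | 63 + 84 + 30 = 177 (2.19) |

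If the control window were instead counted from the last day of Cycle 3, it would be 114 days, and the largest ratio would be 198/114 = 1.74.

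**Mean ibrutinib window.** Let f be the share of three-cycle completers who finish monotherapy. The mean is W = 114 + 84f: 139.2 days at f = 0.3, 164.4 at f = 0.6 (ratio to control 1.73), and 198 at f = 1. The documents give no value for f. The 60% response rate of the pediatric RICE study in Protocol 1.2 motivates f = 0.6. In that study 6 of 20 subjects went on to consolidation; if all six were among the 12 responders, 6/20 = 0.3 is left.

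**Model with no ibrutinib effect.** Both arms have the same event risk to Day 95 and r times that risk afterwards. The value of r is an assumption.

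Exposure-adjusted rate ratio, with all window time in the denominator: [95 + r(W − 95)] / W.

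| r | f = 0.3 | f = 0.6 | f = 1 |
|---|---|---|---|
| 0.1 | 99.42/139.2 = 0.71 | 101.94/164.4 = 0.62 | 105.3/198 = 0.53 |
| 0.5 | 117.1/139.2 = 0.84 | 129.7/164.4 = 0.79 | 146.5/198 = 0.74 |
| 1 | 1.00 | 1.00 | 1.00 |
| 1.5 | 161.3/139.2 = 1.16 | 199.1/164.4 = 1.21 | 249.5/198 = 1.26 |

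Crude percentage with at least one event, for control incidence p by Day 95. The extra days are 114 − 95 = 19 without monotherapy and 198 − 95 = 103 with it:

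1 − [(1 − f)(1 − p)^(1 + 19r/95) + f(1 − p)^(1 + 103r/95)]

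At f = 0.6:

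| Control p | r = 0.1 | r = 0.5 |
|---|---|---|
| 20% | 21.3% (ratio 1.06) | 26.2% (1.31) |
| 50% | 52.4% (1.05) | 60.7% (1.21) |
| 95% | 95.9% (1.01) | 97.9% (1.03) |

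**Effect of the undefined denominator.** If person-time stops at the first event, the rate ratio at f = 0.6 and r = 0.1 to 0.5 is 0.65 to 0.81 for p = 20%, but 0.92 to 0.97 for p = 95%. The choice of denominator alone can remove most of the effect for common events.

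**After the change.** Cutting both arms at the same day makes the nominal windows equal. Under no ibrutinib effect, the crude percentages then agree and the rate ratio is 1.00 for every r.

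**The case against.** Several points on the other side stand.

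- A reader might infer that the ibrutinib arm as a whole is observed for 198 days. It is not. That figure needs a response of PR or better, three completed cycles and all monotherapy, with no progression, toxicity stop, new therapy or conditioning. Protocol 9.1.3 lets a subject in confirmed CR after two cycles go to transplant, which shortens the window in either arm. Likewise, 95 days applies only to control subjects who complete three cycles.
- A reader might infer that the exposure-adjusted rates must be biased in favour of ibrutinib. The documents contain no adverse event rate for the monotherapy period. The bias vanishes under constant risk and reverses if later risk is higher. Lower later risk is plausible, because Protocol 1.2 reports severe but reversible myelosuppression in almost all RICE subjects, but it is not quantified.
- A reader might infer that every crude table is materially inflated. The SAP tabulates subjects with at least one event, and that percentage saturates. For summaries near 95% the distortion is only 1% to 3% in relative terms.
- Overall survival already compares all deaths by arm without a treatment window, and other malignancies are followed beyond treatment in both arms.
- Safety is descriptive, and enrollment stopped after the interim analysis with no new safety concerns (Protocol 11.9.1).

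None of this supplies an adverse event comparison over matched time. Descriptive status does not help, since no other comparison is planned. Overall survival does not replace a comparison of on-treatment deaths, Grade 3 or worse events or hemorrhage, the last being the protocol's named event of special interest (Protocol 12.3.3).

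**Conclusion.** The concern holds in a limited form. For subjects who complete three cycles, the windows are unequal by design: about 95 days in control against 114 to at most 198 on ibrutinib, a ratio of 1.2 to 2.1 with 28-day cycles. No planned table corrects for this.

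Crude percentages and the 6.3 death summary tend to overstate ibrutinib toxicity, chiefly for less frequent events. The exposure-adjusted rates, where planned, would understate it if events concentrate in the CIT cycles. The size is not fixed by the documents. It rests on the share finishing monotherapy, the later risk relative to the CIT period, the unstated denominator, and the reading that last dose includes monotherapy. If monotherapy were excluded, the gap would shrink to 114 against 95 days, and later events would count only if judged drug-related or otherwise caught by the TEAE definition.

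The documents do not support the claim that ibrutinib's toxicity will be misstated by a known amount, or that the two kinds of table are certain to err in opposite directions. They do support the claim that the plan as written gives no like-for-like safety contrast for a stated objective.

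**What to change.** 1. Add to SAP Table 4 and Section 6.3 a comparison of both arms over a common window, for TEAEs, Grade 3 or worse TEAEs, serious TEAEs, hemorrhage and deaths. Use either the combination phase, in line with the Treatment Phase wording of Protocol 11.7, or a fixed day such as Day 95 from first dose. Cut it at subsequent therapy or conditioning, and state whether the cut applies to deaths, because 6.3 does not mention it. Do not anchor the window to the last CIT dose: that date arises after randomization and can differ by arm through delays or early stopping.
2. Tabulate monotherapy-period events separately for the ibrutinib arm.
3. Define the denominator of the exposure-adjusted rates: all window time or time to first event, and whether the 30 days after last dose count.
4. Reconcile the TEAE definitions in SAP 6.1.1 and Protocol 11.7, say whether last dose includes monotherapy, and record any departure in SAP Section 9.

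The cost is a few more descriptive tables from dosing and onset dates already collected. A common window equalizes nominal length only; early cuts for new therapy or transplant can still differ by arm, so their number should be shown beside the tables.
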